Subject Recruitment: FND, other somatoform symptoms and depression patients will be recruited by [name] and collaborators from neurology and psychiatry clinics at the Massachusetts General Hospital(MGH). Patients may also be recruited from inpatient services at the MGH. Healthy subjects will be recruited by advertisement.

Note: all study procedures except recruitment will occur at the MGH.

b. Source of subjects and recruitment methods:

Recruitment of FND, other somatoform symptoms, and/or depression subjects will occur through physician referral at outpatient Neurology and Psychiatry departments at the MGH. Flyers advertising the study may be posted in the neurology and psychiatry centers. A recruitment letter may be mailed to potential research subjects who are referred by their physicians for possible study participation. Referring physicians may also be offered the opportunity to email patients the referral letter via SEND SECURE partners email or through patient gateway. Patients who express interest in this research study may be approached in person in the outpatient clinics or inpatient wards. Note that [name] will directly oversee patient recruitment from MGH.

Control subjects and individuals with depression will be recruited by advertisement (including from online websites such as Craigslist.com, <http://clinicaltrials.partners.org> and email lists) and posted flyers around Boston.

All subjects who have agreed to learn more about this research study will be approached in person or contacted by telephone and/or mail with a subsequent confirmation of eligibility and desire to participate in our study prior to informed consent and scheduling.

To aid subject identification, the medical records of patients admitted to the inpatient neurology service and those scheduled for the post-diagnosis outpatient epilepsy/neuropsychiatry/behavioral neurology clinic will be reviewed to enable investigators to approach clinicians about potential appropriate research referrals.

IV. Subject Enrollment

a. Methods of Enrollment:

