4. Follow-up clinical and psychological questionnaires at approximately 6 months, 12 months, and 24 months (FND Subjects Only).

Subjects may participate in this study for a maximum of 8-9 hours for the initial assessment (1-3). If subjects, elect to participate in the follow-up questionnaires, an additional approximately 2 hours of participation is expected for each session. Subjects participating as healthy volunteers will complete an abbreviated set of self-report questionnaires (2), and may participate in this study for a maximum of 6 hours for the initial assessment (1-3).

b. Method for obtaining informed consent:

Written informed consent will be obtained from the patient or normal subject prior to his/her participation. Consent will be obtained by designated laboratory members with prior explicit training in consent administration. The consent form will be discussed in detail with the subject; the form will be reviewed item by item to ensure an understanding of the purposes and potential risks of the study, including its investigational nature. Subjects will be allowed to read and review the consent in full at their leisure before agreeing to participate. Only patients capable of giving informed consent will be studied.

As noted, participants will complete most psychologic assessments on a separate day from MRI scanning (see detailed list below).

Subjects will be reimbursed 50 dollars for their participation in our detailed psychologic assessment and 50 dollars for participation in our neuroimaging study with brief additional psychologic assessment. Subjects will also be reimbursed an additional 25 dollars for participation in each follow-up assessment. Subjects will also be reimbursed for parking via a parking voucher at both the MGH main campus and the Charlestown sites.

c. Treatment assignment and randomization:

This segment is not applicable to our study because no treatment is offered.

V. Study Procedures

a. Study visits and parameters to be measured:

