The self-report psychometrics collect data on variables such as impulsivity, depression dissociation, psychological trauma, resilience, personality, somatization, attachment, pain catastrophizing, reading ability, handedness and participant specific FND characteristics. Clinician administered psychometrics provide evidence for co-morbid psychiatric conditions while our focused chart review will help collect subject specific FND characteristics, risk factor qualification, review of prior diagnostic evaluations, and review of prior and current treatment strategies. Blood Oxygenation Level-Dependent contrast is measured during functional imaging to reflect changes in venous deoxyhemoglobin associated with neuronal activity. Volumetric quantification will be obtained from SPGR images and white matter tracts will be delineated using diffusion tensor imaging.

b. Study Endpoints

Study endpoint is recruitment of enough participants to comply with our power analysis (30 for each subject group).

c. Statistical Methods**Regions of Interest:****Functional Connectivity Analyses:**

Functional connectivity analyses will be performed using region of interest (seed-based) and whole brain data driven approaches(72-74). Correlational analyses will also be performed to assess associations between connectivity patterns and psychometric measures of interest.

Volumetric Analyses:

High-resolution T1-MRI images will be analyzed using semi-automated quantitative techniques such as voxel-based morphometry(15) and cortical thickness analyses(14, 75). Correlational analyses will also be performed to assess associations between volumetric patterns and psychometric measures of interest.

d. Power Analysis:

Based on neuroimaging studies in other neuropsychiatric populations(24, 76, 77), it is estimated that regions-of-interest will have a mean BOLD signal group difference of 0.7 with a standard deviation of 0.95. For a power of 0.8, approximately 60 total subjects would be needed. We are now adding plans for study replication which will include the need for 60 subjects in each additional study arm. Given that comparisons may include FND vs. Healthy subjects (30 in each group) as well as comparisons between PNES vs. Healthy Subjects, FMD vs. Healthy Subjects, and Functional Weakness Patients vs. Healthy Subjects a total of 30 subjects in each patient group and healthy subject group will be recruited.

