RF Antenna Effects. If metal wires or electrodes are attached to a person being imaged, radiofrequency signals from the MR scanner may conceivably induce sufficient electrical currents in the wires to cause burns where the wires or electrodes contact the skin. If wires or electrodes are present, the scanner operator will inspect and arrange them to minimize the risk of induced currents.

d. Psychosocial (non-medical) risks:

The possibility of invasion of privacy is a risk in this study: Neurologic and psychiatric information will be obtained from the subject, referring physician and medical record. We feel that this is a minimal risk as every effort will be taken to ensure the confidentiality of this information. Only individuals specifically designated for chart review with prior HIPPA training will be allowed access to patient records. All of the information will be collected, de-identified with a subject identification number and collected in a sensitive and respectful manner. A computer-based document and/or manual linking subject identification numbers with subject identity will be stored securely in the laboratory.

e. Radiation Risks:

No ionizing radiation will be used in this study.

VIII. Potential Benefits

a. Potential benefits to participating individuals:

Subjects will not receive any explicit or intended direct benefit from their participation. However, in our experience, patients have often reported that they found the studies interesting and meaningful. They expressed their sentiments with the knowledge that they would not receive any explicit or intended direct benefit from their participation.

b. Potential benefits to society:

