The conditions and symptoms studied in this protocol impair quality of life and result in tremendous costs to society in terms of medical care and disability. As they are brain disorders, a neurobiological approach is the most effective means of learning more about them. The functional and structural neuroimaging techniques used in these studies are the only way to gain this information on an in vivo, systems level. The study represents a careful integration of, and bridge between, such clinical, neuropsychiatric, neuroscientific approaches and the basic behavioral neuroscientific approaches that can provide vital mechanistic information. Focusing upon the neurobiological and neuropsychological processes implicated in symptomatology is an important and direct way of increasing our understanding. Such an understanding provides a necessary foundation for the development of more targeted diagnostic, preventative, and therapeutic approaches to FND.

IX. Monitoring and Quality Assurance

a. Independent monitoring of source data/Safety Monitoring:

Because no clinical diagnosis will be made as part of this study, no interventions will be used, and procedures have been shown to be safe, an independent data safety monitoring board (DSMB) will not be established. The PI, co-investigators and study coordinator will continuously provide oversight to ensure that participants are not exposed to unnecessary or unreasonable risks and that the study is being conducted according to highest scientific and ethical standards.

b. Outcomes monitoring:

Diagnostic and behavioral forms are prepared by a researcher in subject-specific packets. Data are entered into an electronic database, checked against original instruments for inconsistencies, and corrected. Functional scans are analyzed daily to assure proper data acquisition and data quality.

All data will be analyzed and assessed by the PI, co-investigators, and members of the research lab to assure quality and accordance with the IRB-approved protocol.

c. Adverse event reporting guidelines:

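### The plan does not mask diagnostic group, or fix criteria, for scan exclusion, run selection and semi-automated T1 processing

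*Combined protocol and SAP*

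**What the plan says.** Section IX.b, Outcomes monitoring, assigns the work to the study team: "All data will be analyzed and assessed by the PI, co-investigators, and members of the research lab to assure quality". The same section says "Functional scans are analyzed daily to assure proper data acquisition and data quality". It names no person for that check and gives no criterion or keep/drop rule.

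Under Rest Task Procedure in V.e, each subject has one to four resting acquisitions of up to 10 minutes. No rule says which of them enter the analysis. In VI.c, Volumetric Analyses, structural images are handled with "semi-automated quantitative techniques such as voxel-based morphometry" and cortical thickness methods. No editing procedure is described.

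The team also has contact with subjects. In IV.b, "Consent will be obtained by designated laboratory members with prior explicit training in consent administration". In III.a, "FND, other somatoform symptoms and depression patients will be recruited by [name] and collaborators from neurology and psychiatry clinics".

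The nearest thing to masking is a privacy measure in VII.d, where information is "de-identified with a subject identification number". The key is kept in-house: "A computer-based document and/or manual linking subject identification numbers with subject identity will be stored securely in the laboratory".

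In section II, SA1 predicts reduced connectivity between OFC, ACC and amygdala in patients, and otherwise only abnormal connectivity across wider networks. SA2 predicts structural alterations and gives no direction.

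**The concern.** This is an open comparison of diagnostic groups. Between the scanner and the SA1 and SA2 results, human discretion enters mainly through which scans are usable, which runs are used, and what is corrected during processing. The plan neither bounds these choices by criteria nor separates them from knowledge of group.

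If such choices follow both group and the measured value, they can produce or enlarge a difference. In SA1 that difference could favour the predicted direction. In SA2 it could appear as an alteration of either sign, which the hypothesis would also accept. Afterwards a reader could not separate selective retention from a true effect. Masking is practical here in a way that it is not for the clinical interviews, because subject numbers already exist.

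**Working it through.** **1. The plan's own sample size.** VI.d gives a difference of 0.7, SD 0.95, power 0.8 and about 60 subjects, 30 per group. Alpha and sidedness are not stated; I assume two-sided 0.05.

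- Standardised difference: 0.7 / 0.95 = 0.737.
- Normal approximation: n per group = 2 × (1.960 + 0.842)² / 0.737² ≈ 28.9, so 29 per group and 58 in total.
- Exact two-sample t-test: 29.9, so 30 per group and 60 in total, with power 80.1%.

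The stated figure is reproduced. One-sided 0.05 gives 46 in total and does not match.

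**2. Effect of exclusions when there is no true difference.** The documents give no exclusion rate, so I assume 1 to 3 scans of 30. Two normal groups of 30 are simulated with equal means. Scans are removed by the rule shown, and a two-sided t-test at 0.05 is applied. A contrary scan is a high value in patients or a low value in healthy subjects. Under weak selection, drops are random within the contrary half of the group.

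| Rule for dropping scans | 1 of 30 | 2 of 30 | 3 of 30 |
|---|---|---|---|
| Patients only, unrelated to outcome | 0.05 | 0.05 | 0.05 |
| Patients only, weak selection | 0.05 | 0.05 | 0.06 |
| Both groups, weak selection | 0.05 | 0.06 | 0.09 |
| Patients only, most contrary scans | 0.06 | 0.09 | 0.13 |
| Both groups, most contrary scans | 0.10 | 0.21 | 0.36 |

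For the two most-contrary rules at 3 of 30, the false mean difference is about −0.18 (patients only) and −0.35 (both groups) on the SD 0.95 scale. The planned effect is 0.7. Nearly all of these false positives fall in the predicted direction: 0.12 of 0.13, and practically all of 0.36.

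**3. Larger groups.** III.a lists 120 per main group. With the same 10% dropped (12 of 120, patients only), the rate is 0.05 when drops are unrelated to outcome, 0.10 under weak selection and 0.35 when the most contrary scans go. The 10% is an assumption.

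**4. After the fix.** If drops are unrelated to outcome within each group, the error rate stays near 0.05 (simulated 0.049 with 3 of 30 dropped per group). What remains is lost power: 75.7% at 27 per group against 80.1% at 30.

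**The case against.** The best reply is that much of the worry is read into silence. No section says who knows the group when scans are checked. Subject numbers are used, and whether they reveal group is not stated. The sentence in IX.b goes on to compliance with the IRB-approved protocol, so it is a general quality statement and not a procedure for dropping scans. The daily check is described as serving acquisition and data quality, and nothing says that it computes the hypothesised connectivity. Knowing the group does not by itself inflate error: the first row of the table stays at 0.05.

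All of that stands, and it limits the point. A reader might infer that group is openly known to those judging scans, or that the people who recruit and interview subjects also make those judgements. The documents support neither. They show overlap at laboratory level only, since laboratory members take consent and also assess data. A reader might also infer that T1 edits could drift toward the directional hypothesis. They cannot, because the direction belongs to the OFC, ACC and amygdala connectivity hypothesis and SA2 has none. Manual edits themselves are implied by the term semi-automated and are not described.

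The reply does not supply a safeguard. The sections where masking, exclusion criteria, run selection or editing rules would belong (VI.c and IX.b) contain none, and the linking key is held in the laboratory that assesses the data.

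**Conclusion.** The point holds as a gap in the plan. Masking of group is not provided for, and no criteria are set, at the steps where scans, runs and processing involve judgement. It should be closed because it lies on the route to the primary result and closing it is cheap.

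The size is uncertain. At 3 of 30 dropped, the false-positive rate may be anywhere from about 0.05 to about 0.36. The figures assume normal outcomes, one two-sided 0.05 test and the exclusion counts shown. Everything above 0.05 requires exclusions that track the outcome. It would be wrong to take the 0.13 or the 0.35 for patient-only exclusion as an upper bound, because selection in both groups gives more. It would be equally wrong to take either as an estimate for this study, because weak selection gives much less. Nothing here shows that any decision was or will be biased.

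**What to change.** Add to IX.b and VI.c:

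- Image files carry a code that does not reveal group. The linking key is not available to those doing quality control or editing until the quality log is locked.
- Scan and run inclusion, including the choice among the one to four resting acquisitions, follows motion and quality criteria fixed before any group result is seen.
- Existing laboratory members complete and lock all inclusion decisions and any manual edits, working on coded files in mixed group order, before the group key is merged.
- Exclusions are reported by group.

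The daily acquisition check can continue as described, kept separate from the final inclusion decision.

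The cost is recoding files, having someone hold the key apart, and a short delay before group results are available. No extra reader or study procedure is needed.
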